#### Appendix 4. Selected Medical History

Number and percentage of subjects with selected medical history of Diabetes Mellitus, Hypertension, Cardiovascular Disease, and Hyperlipidemia will be summarized by treatment as baseline disease characteristics. A subject who had medical history of one of these diseases is a subject who experience at least one of the following events:

- At least 1 medical history record with MedDRA PT (mh.MDRPT) in the following selected PT listing for the corresponding disease with start date on or prior to the DB phase first dose date.
- At least 1 AE record with MedDRA PT (ae.MDRPT) in the following selected PT listing for the corresponding disease with start date on or prior to the DB phase first dose date.
- At least 1 concomitant medications record with medication class and indication in the following selected listing for the corresponding disease with start date on or prior to the DB phase first dose date.

If the start date is incomplete but the month and year (or year alone) of the start date is the same as or before the month and year (or year alone) of the first dosing date of randomized study drug, the event will be included. If the start date is completely missing, the event will be included.

Four variables (ie, DIABETES, HTENSION, CARDDIS, and HLIPDEM) will be added to raw Medical History and Adverse Events datasets. A medical history or an AE record will be flagged for a disease of interest if its MedDRA PT included in the prespecified PT list for the corresponding disease of interest, which include all PTs from the narrow or broad search of the following SMQs under MedDRA 19.1 provided by Gilead DSPH and reviewed by Gilead medical monitors.

Disease of Interest	SMQ Source				
Diabetes Mellitus (DIABETES)	Hyperglycaemia/new onset diabetes mellitus (SMQ) Narrow Scope Term				
Hyperlipidemia (HLIPDEM)	Dyslipidaemia (SMQ)				
Hypertension (HTENSION)	Hypertension (SMQ)				
	Ischaemic central nervous system vascular conditions (SMQ) Narrow Scope Term				
Cardiovascular disease (CARDDIS)	Myocardial infarction (SMQ) Narrow Scope Term				
(C/HDDIS)	Other ischaemic heart disease (SMQ) Narrow Scope Term				

Similarly, two variables (ie, DRUGF and DRUGTYP) will be added to raw Concomitant Medication dataset. A concomitant medication record will be flagged for a disease of interest if its medication class and indication included in the following listing for the corresponding disease of interest.

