147	DRUGS USED IN DIABETES	UNCONTROLLED DM2	INSULIN DETEMIR
148	UNSPECIFIED HERBAL AND TRADITIONAL MEDICINE	HERBAL SUPPLEMENT	GLYCINE MAX EXTRACT
149	LIPID MODIFYING AGENTS	DIABETES MELLITUS TYPE II	PRAVASTATIN

	Medication Class (WHOATC2)	Indication (CMINDC)	WHOGEN
Card	iovascular (CARDDIS)		
1	AGENTS ACTING ON THE RENIN ANGIOTENSIN SYSTEM	ACUTE MYOCARDIAL INFARCTION	IRBESARTAN
2	AGENTS ACTING ON THE RENIN ANGIOTENSIN SYSTEM	CARDIOMYOPATHY	LISINOPRIL
3	AGENTS ACTING ON THE RENIN ANGIOTENSIN SYSTEM	CARDIOMYOPATHY	RAMIPRIL
4	AGENTS ACTING ON THE RENIN ANGIOTENSIN SYSTEM	CONGESTIVE HEART FAILURE	LISINOPRIL
5	AGENTS ACTING ON THE RENIN ANGIOTENSIN SYSTEM	CORONARY ARTERY DISEASE	RAMIPRIL
6	BETA BLOCKING AGENTS	ACUTE MYOCARDIAL INFARCTION	BISOPROLOL FUMARATE
7	BETA BLOCKING AGENTS	ANTI ARRHYTHMIC	SOTALOL
8	BETA BLOCKING AGENTS	ATHEROSCLEROTIC HEART DISEASE OF NATIVE CORONARY ARTERY WITHOUT ANGINA PECTORIS	CARVEDILOL
9	BETA BLOCKING AGENTS	ATRIAL FIBRILATION	ATENOLOL
10	BETA BLOCKING AGENTS	ATRIAL FIBRILATION	METOPROLOL
11	BETA BLOCKING AGENTS	ATRIAL FIBRILLATION	METOPROLOL
12	BETA BLOCKING AGENTS	ATRIAL FIBRILLATION	METOPROLOL TARTRATE
13	BETA BLOCKING AGENTS	ATYPICAL CHEST PAIN	LABETALOL
14	BETA BLOCKING AGENTS	BRUGADA SYNDROME	BISOPROLOL
15	BETA BLOCKING AGENTS	CAD	METOPROLOL SUCCINATE
16	BETA BLOCKING AGENTS	CADRIOMYOPATHY	BISOPROLOL
17	BETA BLOCKING AGENTS	CARDIAC PACEMAKER INSITU	METOPROLOL
18	BETA BLOCKING AGENTS	CARDIAC PROPHYLAXIS	CARVEDILOL
19	BETA BLOCKING AGENTS	CARDIOMYOPATHY	CARVEDILOL
20	BETA BLOCKING AGENTS	CHEST TIGHTNESS	BISOPROLOL
21	BETA BLOCKING AGENTS	CONGESTIVE HEART FAILURE	ATENOLOL
22	BETA BLOCKING AGENTS	CONGESTIVE HEART FAILURE	CARVEDILOL
23	BETA BLOCKING AGENTS	CONTROLLED HYPERTENSION	TENORETIC
24	BETA BLOCKING AGENTS	CORONARY ARTERY DISEASE	METOPROLOL
25	BETA BLOCKING AGENTS	CORONARY ARTERY DISEASE	METOPROLOL SUCCINATE
26	BETA BLOCKING AGENTS	CORONARY ARTERY STENOSIS	METOPROLOL
27	BETA BLOCKING AGENTS	DYSRHYTHMIA	BISOPROLOL FUMARATE
28	BETA BLOCKING AGENTS	HEART FAILURE AND HYPERTENSION	CARVEDILOL
29	BETA BLOCKING AGENTS	INTERMITTENT ARRHYTHMIA	BISOPROLOL
30	BETA BLOCKING AGENTS	MITRAL INSUFFICIENCY	BISOPROLOL

	Medication Class (WHOATC2)	Indication (CMINDC)	WHOGEN
31	BETA BLOCKING AGENTS	PREVENTATIVE FOLLOWING ACUTE MYCARDIAL INFARCTION	BISOPROLOL
32	BETA BLOCKING AGENTS	SICK SINUS SYNDROME	METOPROLOL
33	BETA BLOCKING AGENTS	SUPRA VENTRICULAR TACHYCARDIA	ATENOLOL
34	BETA BLOCKING AGENTS	SUPRAVENTRICULAR TACHYCARDIA	ATENOLOL

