35	BETA BLOCKING AGENTS	SUPRAVENTRICULAR TACHYCARDIA	METOPROLOL
36	BETA BLOCKING AGENTS	TACHYCARDIA	ATENOLOL
37	CALCIUM CHANNEL BLOCKERS	CORONARY ARTERY DISEASE	AMLODIPINE
38	CALCIUM CHANNEL BLOCKERS	CORONARY ARTERY DISEASE	AMLODIPINE BESILATE
39	CALCIUM CHANNEL BLOCKERS	SUPRAVENTRICULAR TACHYCARDIA	VERAPAMIL
40	CARDIAC THERAPY	ACUTE MYOCARDIAL INFARCTION	AMIODARONE HYDROCHLORIDE
41	CARDIAC THERAPY	ACUTE MYOCARDIAL INFARCTION	ISOSORBIDE DINITRATE
42	CARDIAC THERAPY	ALLERGIC REACTION	EPINEPHRINE
43	CARDIAC THERAPY	ANGINA	GLYCERYL TRINITRATE
44	CARDIAC THERAPY	ANGINA PECTORIS	RANOLAZINE
45	CARDIAC THERAPY	ANGIOGRAM/STENT	ADENOSINE
46	CARDIAC THERAPY	ANGIONEUROTIC EDEMA	EPINEPHRINE
47	CARDIAC THERAPY	ANTIARRHYTHMIC AGENT	FLECAINIDE ACETATE
48	CARDIAC THERAPY	ATRIAL FIBRILLATION	DIGOXIN
49	CARDIAC THERAPY	ATRIAL FIBRILLATION	FLECAINIDE ACETATE
50	CARDIAC THERAPY	ATYPICAL CHEST PAIN	GLYCERYL TRINITRATE
51	CARDIAC THERAPY	CAD	UBIDECARENONE
52	CARDIAC THERAPY	CARDIOMYOPATHY	ISOSORBIDE DINITRATE
53	CARDIAC THERAPY	CARDIOVASCULAR DISEASE PROPHYLAXIS	UBIDECARENONE
54	CARDIAC THERAPY	CHEST PAIN	GLYCERYL TRINITRATE
55	CARDIAC THERAPY	CHEST PAINS	GLYCERYL TRINITRATE
56	CARDIAC THERAPY	CHESTPAIN	GLYCERYL TRINITRATE
57	CARDIAC THERAPY	CORONARY ARTERY DISEASE	GLYCERYL TRINITRATE
58	CARDIAC THERAPY	CORONARY ARTERY DISEASE	ISOSORBIDE MONONITRATE
59	CARDIAC THERAPY	HYPERLIPIDEMIA	ISOSORBIDE MONONITRATE
60	CARDIAC THERAPY	NSTEMI	ISOSORBIDE DINITRATE
61	CARDIAC THERAPY	PERIOP STRESS TEST	REGADENOSON
62	CARDIAC THERAPY	PROPHYLAXIS	GLYCERYL TRINITRATE
63	CARDIAC THERAPY	PROPHYLAXIS FOR CARDIAC HEALTH	UBIDECARENONE

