## Statistical Analysis Plan – End of Blinded Treatment Phase Analysis

	Medication Class (WHOATC2)	Indication (CMINDC)	WHOGEN	
64	CARDIAC THERAPY	SUPRAVENTRICULAR TACHYCARDIA	ADENOSINE	
65	CARDIAC THERAPY	UNCONTROLLED DIABETES MELLITUS 2	AMIODARONE HYDROCHLORIDE	
66	CARDIAC THERAPY	UNCONTROLLED DIABETES MELLITUS 2	GLYCERYL TRINITRATE	
67	DIURETICS	ACUTE RESPIRATORY FAILURE	FUROSEMIDE	
68	DIURETICS	AORTIC VALVE REPLACEMENT	FUROSEMIDE	
69	DIURETICS	CHF	BUMETANIDE	
70	DIURETICS	CHF	HYDROCHLOROTHIAZIDE	
71	DIURETICS	CHF	METOLAZONE	
72	DIURETICS	CONGESTIVE HEART FAILURE	BUMETANIDE	
73	DIURETICS	CONGESTIVE HEART FAILURE	FUROSEMIDE	
74	DIURETICS	CONGESTIVE HEART FAILURE	HYDROCHLOROTHIAZIDE	
75	DIURETICS	CONGESTIVE HEART FAILURE	METOLAZONE	
76	DIURETICS	CONGESTIVE HEART FAILURE	SPIRONOLACTONE	
77	DIURETICS	CORONARY ARTERY DISEASE	HYDROCHLOROTHIAZIDE	
78	DIURETICS	CORONARY ARTERY DISEASE.	FUROSEMIDE	
79	DIURETICS	ELEVATION OF BLOOD PRESSURE	FUROSEMIDE	
80	DIURETICS	MITRAL INSUFFICIENCY	TORASEMIDE	
81	DIURETICS	TRANSGENGER	SPIRONOLACTONE	
82	LIPID MODIFYING AGENTS	ACUTE MYOCARDIAL INFARCTION	ATORVASTATIN CALCIUM	
83	LIPID MODIFYING AGENTS	ACUTE MYOCARDIAL INFARCTION	OMEGA 3 TRIGLYCERIDES	
84	LIPID MODIFYING AGENTS	ATHEROSCLEROTIC HEART DISEASE OF NATIVE CORONARY ARTERY WITHOUT ANGINA PECTORIS	SIMVASTATIN	
85	LIPID MODIFYING AGENTS	BASILAR ARTERY THROMBUS	ATORVASTATIN CALCIUM	
86	LIPID MODIFYING AGENTS	CAD	PRAVASTATIN SODIUM	
87	LIPID MODIFYING AGENTS	CAD	ROSUVASTATIN CALCIUM	
88	LIPID MODIFYING AGENTS	CARDIAC PROPHYLAXIS	ATORVASTATIN	
89	LIPID MODIFYING AGENTS	CARDIAC PROPHYLAXIS	FISH OIL	
90	LIPID MODIFYING AGENTS	CARDIOVASCULAR PROPHYLAXIS	ATORVASTATIN CALCIUM	
91	LIPID MODIFYING AGENTS	CHEST TIGHTNESS	ATORVASTATIN	

	Medication Class (WHOATC2)	Indication (CMINDC)	WHOGEN					
Нуре	Hyperlipidemia (HLIPDEM)							
1	AGENTS ACTING ON THE RENIN-ANGIOTENSIN SYSTEM	HYPERTRIGLYCERIDEMIA	LISINOPRIL					
2	ANTIHYPERTENSIVES	HYPERCHOLESTEROLEMIA	DOXAZOSIN MESILATE					
3	CARDIAC THERAPY	HYPERCHOLESTEROLEMIA	UBIDECARENONE					
4	LIPID MODIFYING AGENTS	ABNORMAL LIPIDS	ATORVASTATIN					
5	LIPID MODIFYING AGENTS	CARDIAC PROPHYLAXIS	ROSUVASTATIN					
6	LIPID MODIFYING AGENTS	CHOLESTEROL	ROSUVASTATIN					
7	LIPID MODIFYING AGENTS	CHOLESTEROL	ROSUVASTATIN CALCIUM					
8	LIPID MODIFYING AGENTS	CHOLESTEROLEAMIA	ATORVASTATIN					
9	LIPID MODIFYING AGENTS	CHOLESTERORL	ROSUVASTATIN CALCIUM					
10	LIPID MODIFYING AGENTS	CORONARY ARTERY DISEASE	ATORVASTATIN					

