11	LIPID MODIFYING AGENTS	CORONARY ARTERY DISEASE	EZETIMIBE					
12	LIPID MODIFYING AGENTS	CORONARY ARTERY DISEASE	FENOFIBRATE					
13	LIPID MODIFYING AGENTS	CORONARY ARTERY DISEASE	ROSUVASTATIN CALCIUM					
14	LIPID MODIFYING AGENTS	CORONARY ARTERY DISEASE PROPHYLAXIS	ATORVASTATIN					
15	LIPID MODIFYING AGENTS	DIET SUPPLEMENT	FISH OIL					
16	LIPID MODIFYING AGENTS	DIETARY SUPPLEMENT	FISH OIL					
17	LIPID MODIFYING AGENTS	DIETARY SUPPLEMENTS	FISH OIL					
18	LIPID MODIFYING AGENTS	DYSLIPEDEMIA	ROSUVASTATIN CALCIUM					
19	LIPID MODIFYING AGENTS	DYSLIPIDAEMIA	ATORVASTATIN					
20	LIPID MODIFYING AGENTS	DYSLIPIDEMIA	ATORVASTATIN					
21	LIPID MODIFYING AGENTS	DYSLIPIDEMIA	FENOFIBRATE					
22	LIPID MODIFYING AGENTS	DYSLIPIDEMIA	FISH OIL					
23	LIPID MODIFYING AGENTS	DYSLIPIDEMIA	GEMFIBROZIL					
24	LIPID MODIFYING AGENTS	DYSLIPIDEMIA	PRAVASTATIN					
25	LIPID MODIFYING AGENTS	DYSLIPIDEMIA	ROSUVASTATIN					
26	LIPID MODIFYING AGENTS	DYSLIPIDEMIA, WORSENING	ROSUVASTATIN					
27	LIPID MODIFYING AGENTS	DYSLIPIDERMIA	PRAVASTATIN					

	Medication Class (WHOATC2)	Indication (CMINDC)	WHOGEN	
28	LIPID MODIFYING AGENTS	ELEVATED CHOLESTEROL	SIMVASTATIN	
29	LIPID MODIFYING AGENTS	ELEVATED LIPIDS	ATORVASTATIN	
30	LIPID MODIFYING AGENTS	ELEVATED LIPIDS	ATORVASTATIN CALCIUM	
31	LIPID MODIFYING AGENTS	ELEVATED TRIGLYCERIDES	FISH OIL	
32	LIPID MODIFYING AGENTS	HIGH CHOLESTEROL	ATORVASTATIN	
33	LIPID MODIFYING AGENTS	HIGH CHOLESTEROL	ATORVASTATIN CALCIUM	
34	LIPID MODIFYING AGENTS	HIGH CHOLESTEROL	GEMFIBROZIL	
35	LIPID MODIFYING AGENTS	HIGH CHOLESTEROL	LOVASTATIN	
36	LIPID MODIFYING AGENTS	HIGH CHOLESTEROL	PRAVASTATIN	
37	LIPID MODIFYING AGENTS	HIGH CHOLESTEROL	ROSUVASTATIN CALCIUM	
38	LIPID MODIFYING AGENTS	HIGH CHOLESTEROL	SIMVASTATIN	
39	LIPID MODIFYING AGENTS	HIGH CHOLESTROL	ATORVASTATIN	
40	LIPID MODIFYING AGENTS	HIGH PLASMA LIPIDS	ATORVASTATIN	
41	LIPID MODIFYING AGENTS	HIGH TRIGLYCERIDES	FENOFIBRATE	
42	LIPID MODIFYING AGENTS	HIGH TRIGLYCERIDES AND HYPERCHOLESTEROLEMIA	ATORVASTATIN	
43	LIPID MODIFYING AGENTS	HIPERCOLESTEROLEMIA	ATORVASTATIN	
44	LIPID MODIFYING AGENTS	HIPERCOLESTEROLEMIA	ATORVASTATIN CALCIUM	
45	LIPID MODIFYING AGENTS	HIPERCOLESTEROLEMIA	SIMVASTATIN	
46	LIPID MODIFYING AGENTS	HYERLIPIDEMIA	OMEGA-3-ACID ETHYL ESTER	
47	LIPID MODIFYING AGENTS	HYPERCHOLESTERIMIA	FENOFIBRATE	
48	LIPID MODIFYING AGENTS	HYPERCHOLESTERINAEMIA	ATORVASTATIN	
49	LIPID MODIFYING AGENTS	HYPERCHOLESTERINAEMIA	PRAVASTATIN	

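### Some medication-list rows in SAP Appendices 4 and 11 carry indications that are not the flagged disease, so the descriptive baseline comorbidity percentages can be overstated

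*SAP*

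**What the plan says.** SAP Appendix 4 defines a history of each of four diseases by any one of a medical history term, an adverse event term, or a medication record. The medication route needs only "At least 1 concomitant medications record with medication class and indication in the following selected listing for the corresponding disease", dated on or before first dose in the double-blind phase. The matching rule is stated again further on: "A concomitant medication record will be flagged for a disease of interest if its medication class and indication included in the following listing". The generic drug name is shown in the lists but is not named as a matching key. Incomplete start dates count when the known month or year is compatible, and "If the start date is completely missing, the event will be included".

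On use, Appendix 4 says that the numbers and percentages "will be summarized by treatment as baseline disease characteristics". Appendix 11 repeats the rule and the lists but says only that such subjects will be identified. SAP 5.1 to 5.3, which set out the baseline tables, do not include the four diseases, and SAP 5.4 says general medical history is listed only. Both appendices say the medication lists were reviewed by the sponsor's medical monitors.

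**The concern.** A medication record is a reasonable stand-in for a diagnosis when the stated reason for the drug is the disease. Several rows fail that test. The cardiovascular list accepts epinephrine for "ALLERGIC REACTION". The hyperlipidemia list accepts fish oil as a "DIETARY SUPPLEMENT". The diabetes list accepts a soy extract recorded as a "HERBAL SUPPLEMENT". The cardiovascular list also contains the row "DIURETICS TRANSGENGER SPIRONOLACTONE". Under the stated rule, one such record dated at or before baseline puts the participant in the disease count with nothing else to support it.

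The rows also sit badly with the SAP's own definitions. The diagnosis route for cardiovascular disease uses narrow-scope ischaemic terms (central nervous system, myocardial infarction, other ischaemic heart disease), so allergy or a transgender indication measures something else under the same label. SAP 7.2.3 defines a lipid-modifying medication as that class with a statin name. Fish oil is therefore left out there, yet it establishes hyperlipidemia here.

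At stake is the accuracy of a descriptive table of who was enrolled.

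**Working it through.** The SAP gives no prevalence or person count for these flags, so there is no stated figure to reproduce. The check is a reading of the rule and a count of list rows.

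**Rows whose indication is not the flagged disease** (row numbers as in Appendix 4)

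- Hyperlipidemia, 155 rows. Supplement-only indication: 15, 16, 17, 131, 132, 133, 141, 142, 143, 144, 145, 147, 148, which is 13 rows (13/155 = 8.4%), 8 of them fish oil. Adding 122 (irritable bowel syndrome), 136 (preventive) and 137 (prophylaxis) gives 16 rows; 16/155 = 10.3%. Rows that name a lipid disorder alongside the supplement or preventive use (135, 146) are not counted.
- Cardiovascular disease, 91 rows. Rows 42 (epinephrine, allergic reaction), 46 (epinephrine, angioneurotic edema), 61 (regadenoson, perioperative stress test) and 81 (spironolactone, TRANSGENGER): 4/91 = 4.4%.
- Diabetes, 149 rows. Rows 114 (metformin, nonalcoholic steatohepatitis) and 148 (soy extract, herbal supplement): 2/149 = 1.3%.
- Hypertension, 191 rows. Rows 82 (losartan potassium, hypokalemia), 86 to 88 (renin-angiotensin agents, proteinuria) and 96 (hydralazine, headache): 5/191 = 2.6%.

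These are shares of lookup rows, not of participants. A row may match nobody at baseline or many people.

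**When a percentage changes.** Two conditions must both hold: the record meets the baseline date rule, and the participant has no other qualifying history, adverse event or medication record. An extra row can add a flag but cannot remove one, so any error from these rows runs only toward overcounting.

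**Illustrative size.** With k participants wrongly flagged for one disease, the overall percentage rises by 100 × k / 5387, where 5387 is the Safety Analysis Set size in SAP Appendix 3. The values of k are assumptions.

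- k = 1: 0.02 percentage points
- k = 10: 0.19
- k = 50: 0.93
- k = 100: 1.86

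**Where the flags go.** They do not appear among the covariates (SAP 3.3), the subgroups (SAP 3.4), the efficacy model (SAP 6.2.5) or the bone and renal analyses (SAP 7.3 and 7.4). The lipid sensitivity analysis in SAP 7.2.3 uses its own statin-based definition.

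**The case against.** The strongest reply has four parts.

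- **The lists may reach beyond baseline.** Entries for worsening hypertension, a grade 3 LDL elevation and a perioperative stress test suggest that they were compiled from all medication records, including those started after first dose. Protocol 6.2.1 asks at screening about medications used in the previous 30 days. A one-off drug such as regadenoson may never meet the date rule. This stands: it is a reason not to say that any percentage is wrong, only that it can be.
- **The lists were reviewed medically, and a sensitive case definition is partly judgement.** This stands for borderline rows. Amiodarone and glyceryl trinitrate recorded under uncontrolled diabetes (cardiovascular rows 65 and 66) may well indicate heart disease, and lipid drugs given for coronary disease (hyperlipidemia rows 10 to 13) are defensible. It does not rescue a dietary supplement or an allergic reaction.
- **The summary may not be produced.** SAP 5.2 omits it, 5.4 says listed only and Appendix 11 says only identified. That is an unresolved conflict within the SAP, not an answer to the point.
- **The rule is the same in both arms and looks at pre-dose records.** This stands; these rows give no reason to expect bias in a treatment comparison.

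A reader might infer from the spironolactone row that transgender women on that drug are generally counted as having cardiovascular disease. The documents do not support that. Matching is on class and indication, so this single row of 91 catches only the misspelled indication; any other wording, including the correct spelling, is not caught by it.

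**Conclusion.** The point holds as a matter of list quality. The rule as written can count a participant as having hyperlipidemia, cardiovascular disease, diabetes or hypertension on a record that does not indicate it. Hyperlipidemia is the most exposed, with 16 of 155 rows. The direction is known (overcounting); the size in participants is not, and the range from 0.02 to 1.86 percentage points rests entirely on assumed counts of 1 to 100.

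Two further readings go too far. A reader might conclude that the comorbidity figures will be wrong; that needs record dates and other qualifying records, which the documents do not give. A reader might also conclude that the renal, lipid or bone safety results are misdescribed. The flags feed none of those analyses, and baseline renal and bone measures are tabulated directly under SAP 5.2. The consequence is confined to one descriptive baseline summary, and this is a minor correction.

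**What to change.** Before database finalization:

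1. Screen all four lists in Appendices 4 and 11. Remove rows where neither the drug nor the indication points to the flagged disease, or set the flag from them only when a medical history or adverse event term supports it. The hyperlipidemia supplement rows and cardiovascular rows 42, 46, 61 and 81 are the plain cases, with diabetes row 148.
2. For rows where the drug class is used for the disease but the stated reason is another condition (hypertension rows 82, 86 to 88 and 96, and diabetes row 114), requiring a supporting diagnosis is safer than outright deletion. Rows such as cardiovascular 65 and 66, where the drug itself may indicate the disease, can stay.
3. Regenerate the four flags and record how many participants change status, which supplies the count now missing.
4. State in SAP 5.2 and 5.4 and in both appendices whether the by-treatment summary is produced, and keep one copy of the lists.

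The cost is an edit to lookup lists and a few sentences, plus a rerun of the flags. No new data are needed.

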From the time of obtaining informed consent through the first administration of study drug, record all SAEs, as well as any AEs related to protocol-mandated procedures on the adverse events electronic case report form (eCRF). All other untoward medical occurrences observed during the screening period, including exacerbation or changes in medical history are to be captured on the medical history eCRF. See Section 7 Adverse Events and Toxicity Management for additional details.

6.3. Treatment Assessments Blinded Phase (Weeks 4, 12, and Every 12 Weeks Until the end of blinded treatment phase visit)

The following evaluations are to be completed at the Weeks 4, 12, and every 12 weeks visits until the end of blinded treatment phase visit unless otherwise specified.

All study visits are to be scheduled relative to the Day 1 visit date. Study visits are to be completed within ± 2 days of the protocol-specified visit date based on the Day 1 visit through Week 12 and study visits thereafter completed within ± 14 days of the protocol-specified visit date through the end of blinded treatment phase visit, unless otherwise specified.

Regularly scheduled evaluations will be performed for all participants whether or not they continue to receive study drug, unless otherwise specified.

- Targeted (symptom directed) physical examination (complete physical examination at Weeks 48 and 96 only)
- Review of AEs and changes in concomitant medications, including assessment of whether any STIs were diagnosed and any treatments were received since last visit
- When clinically indicated, vital signs measurement (blood pressure, pulse, respiration rate, and temperature)

- Weight
- STI testing. Participants who test positive for any STI will be treated in accordance with local STI guidelines.
 - Genital, rectal, and pharyngeal examination as appropriate
 - Pharyngeal and rectal swabs for gonorrhea and chlamydia (per local lab). Swabs may be self-administered by the participant at the discretion of the investigator (rectal swab not required at Week 4).
 - Urine sample for gonorrhea and chlamydia (per central lab)
 - Blood sample for syphilis testing (per local lab)
- Fourth generation rapid HIV-1 Ab/Ag or third generation rapid HIV-1 Ab test (**not done for HIV-infected participants**)

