### 7.1.5. Treatment-Emergent Adverse Events

### 7.1.5.1. Definition of Treatment-Emergent Adverse Events

Treatment-emergent adverse events (TEAEs) are defined as 1 or both of the following:

- Any AEs with an onset date on or after the study drug start date and no later than 30 days after permanent discontinuation of the study drug (regardless of study drug interruptions), or
- Any AEs leading to premature discontinuation of study drug.

The TEAE definitions will be applied to the DB phase data and the OLE phase data, separately. When DB phase data are used, AEs onset date will be compared with the DB phase first dose date and last dose date and premature discontinuation of study drug refers to study drug discontinuation in the DB phase. An AE meeting the TEAE criteria will be considered as a TEAE in the DB phase. When OLE phase data are used, AEs onset date will be compared with the OLE phase first dose date and last dose date and premature discontinuation of study drug refers to study drug discontinuation in the OLE phase. An AE meeting the TEAE criteria will be considered as a TEAE in the OLE phase.

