### 7.1.5.2. Incomplete Dates

If the onset date of the AE is incomplete and the AE stop date is not prior to the first dosing date of study drug, then the month and year (or year alone if month is not recorded) of onset determine whether an AE is treatment emergent. The event is considered treatment emergent for the DB phase if both of the following 2 criteria are met:

- The month and year (or year) of the AE onset is the same as or after the month and year (or year) of the first dosing date of study drug, and
- The month and year (or year) of the AE onset is the same as or before the month and year (or year) of the date corresponding to the minimum of

30 days after the date of the DB phase last dose of study drug, and

the OLE phase first dose date minus 1 day.

The event is considered treatment emergent for the OLE phase if both of the following 2 criteria are met:

- The month and year (or year) of the AE onset is **after** the month and year (or year) of the first dosing date of OLE phase study drug, and
- The month and year (or year) of the AE onset is **the same as or before** the month and year (or year) of the date corresponding to 30 days after the date of the last dose of OLE phase study drug.

An AE with completely missing onset and stop dates, or with the onset date missing and a stop date marked as ongoing or on or after the first dosing date of randomized study drug, will be considered to be treatment emergent for the DB phase. In addition, an AE with the onset date missing and incomplete stop date with the same or later month and year (or year alone if month is not recorded) as the first dosing date of the randomized study drug will be considered treatment emergent for the DB phase.

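### The same adverse-event record can count both as baseline disease (SAP Appendices 4 and 11) and as treatment-emergent (SAP 7.1.5), so post-dose events can enter the descriptive baseline summary

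*SAP*

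**What the plan says.** SAP Appendix 4 builds four disease flags that "will be summarized by treatment as baseline disease characteristics". A subject is flagged through any one of three routes: medical history, adverse events or concomitant medication. The second route begins "At least 1 AE record with MedDRA PT (ae.MDRPT") and requires a listed term "with start date on or prior to the DB phase first dose date". An incomplete date qualifies when "the month and year (or year alone) of the start date is the same as or before the month and year (or year alone") of first dose. For a date that is wholly unknown, "If the start date is completely missing, the event will be included". None of these conditions looks at the stop date. Appendix 11 has the same date rules, but says only that such subjects will be identified.

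SAP 7.1.5.1 defines treatment-emergent events by date as "Any AEs with an onset date on or after the study drug start date", up to 30 days after permanent discontinuation. SAP 7.1.5.2 adds incomplete onsets in the first-dose month or year or later, provided that the event had not stopped before first dose. It also adds "An AE with completely missing onset and stop dates, or with the onset date missing and a stop date marked as ongoing", or with a stop on or after first dose. Appendix 12 item 22 repeats these rules for programming.

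Protocol 6.2.2 limits what reaches the adverse-event form before dosing to serious events and events caused by protocol procedures. "All other untoward medical occurrences observed during the screening period, including exacerbation or changes in medical history are to be captured" on the medical history form instead.

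**The concern.** Each date rule leans towards inclusion, and they lean in opposite directions: Appendix 4 resolves doubt as old disease, and 7.1.5 resolves it as a new event. Both apply to the same adverse-event dataset, and nothing in the SAP gives one precedence or removes treatment-emergent events from the flag. A hypertension, glucose or lipid event that began on study could then be reported as a condition the participant brought into the trial, and reported again in the treatment-emergent tables of SAP 7.1.6. At stake is the meaning of a baseline table, which should not be able to contain events that followed treatment, and the consistency of the report.

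**Working it through.** There is no plan figure to reproduce. The check applies both sets of date rules to one record at a time. The example takes first dose on 10 January 2017, with last dose well after the onset dates shown.

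| AE onset | AE stop | Baseline disease (Appendix 4) | Treatment-emergent (7.1.5) |
|---|---|---|---|
| 9 Jan 2017 | ongoing | yes | no |
| 10 Jan 2017 (Day 1) | ongoing | yes | **yes** |
| 11 Jan 2017 | ongoing | no | yes |
| Dec 2016, day unknown | ongoing | yes | no |
| Jan 2017, day unknown | ongoing | yes | **yes** |
| Jan 2017, day unknown | 5 Jan 2017 | yes | no |
| Feb 2017, day unknown | ongoing | no | yes |
| 2016 only | ongoing | yes | no |
| 2017 only | 20 Dec 2017 | yes | **yes** |
| missing | ongoing or missing | yes | **yes** |
| missing | 14 Nov 2018 | yes | **yes** |
| missing | 1 Dec 2016 | yes | no |

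The bold rows meet both definitions. The overlap is not total: incompletely dated or undated events that stopped before first dose are baseline only, and so are partial onsets in an earlier month or year. The table uses date tests only. Under 7.1.5.1 an event that leads to premature discontinuation is treatment-emergent whatever its date.

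How late can an event start and still be labelled baseline?

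- Month and year known: last day of the first-dose month minus first-dose date. The maximum is 31 − 1 = 30 days, for first dose on the 1st of a 31-day month.
- Year only: 31 December of the first-dose year minus first-dose date. SAP Appendix 9 (DBS 1.1) gives enrolment as September 2016 to June 2017. The lag is 121 days for first dose on 1 September 2016, 364 days for 1 January 2017 and 184 days for 30 June 2017. The maximum is 364 days.
- Onset missing: no limit, because neither an onset nor a stop date constrains the flag.

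For scale, SAP Appendix 3 gives 5387 subjects in the Safety Analysis Set. If they are split evenly (an assumption), an arm has 5387 / 2 ≈ 2694, and about 0.01 × 2694 ≈ 27 wrongly flagged participants would move one disease percentage by one point.

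**The case against.** Inclusive handling of incomplete dates is a normal convention in both settings: one rule avoids missing a possible treatment-emergent event, the other avoids missing possible history. The summaries are separate, and the baseline flags drive nothing. They are not covariates (SAP 3.3) or subgroup factors (3.4). Counting Day 1 as baseline also matches SAP 3.8.1, and since dosing may follow the Day 1 visit by up to 24 hours (Protocol 6.2.2), an onset on the first-dose date can precede the dose. All of this stands, and it limits the importance of the point. It does not remove the contradiction, because the conventions meet on the same record and neither yields. The SAP is also stricter elsewhere: under 7.6.3 a missing or year-only end date does not count as baseline F/TDF use.

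A reader might infer that an adverse-event record with an unclear onset is almost always post-dose. The documents support only that it is more likely to be. Protocol 6.2.2 and 7.3.1 keep most pre-dose events off the form, but Protocol 7.1.1 treats worsening of a pre-existing condition as an adverse event, so some of these records may reflect genuine earlier disease.

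A reader might also infer that a baseline hypothesis test is contaminated, or that a real treatment difference would show up as baseline imbalance. Appendix 4 names only a summary by treatment. The four diseases are absent from the list in SAP 5.2 to which the Cochran-Mantel-Haenszel test applies, and only the small overlapping fraction of events could enter.

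**Conclusion.** The inconsistency is real and is written into the rules; it is not a gap that programming would fill. Post-dose events can enter a descriptive baseline summary, and the same event can be reported twice under opposite labels. It is minor. The documents give no number of listed adverse events with Day 1, partial or missing onset, so no count can be stated. The effect is expected to be small, because data queries (Protocol 9.1.6) should leave few undated records and because a participant with a qualifying medical-history or medication record is flagged anyway. No efficacy or alpha-controlled result depends on these flags. The conclusion assumes that both rules are programmed as written. The maximum lags are what the rules allow, not what is known to have happened.

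**What to change.** In Appendices 4 and 11, for the adverse-event route only, exclude any record that is treatment-emergent under 7.1.5. An adverse event would then count as baseline disease only if its onset, complete or partial, is clearly before first dose, or if its stop date is before first dose. The stop-date clause matters: without it, a record with missing or same-month onset that ended before dosing would be neither baseline nor treatment-emergent. Tie the exclusion to the date tests in 7.1.5, since its other limb (events leading to premature discontinuation) carries no date. Keep the inclusive rule for medical-history records.

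At the same time, reconcile Appendix 4 with SAP 5.4, which says that general medical history is only listed.

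The cost is a sentence in each appendix and one condition in the program. The downside is that a pre-dose serious event with unknown onset that is still ongoing, or an event on Day 1 that preceded dosing, would no longer set the flag through the adverse-event route. The other two routes remain open to such participants.
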